Activity	Screen	Pre-op (baseline)	Pre-op after epidural, before bolus	Pre-op after epidural, after bolus/before anesthesia	Intra-op	Post-op Recovery (PACU)	1 hour post-op	Transfer to floor	POD 1	POD 2	POD 3
Informed consent	Х										
Inclusion / Exclusion Criteria	Х										
Medical History	Х										
Randomization		Х									
IV Placement		Х									
Primary measurements(SBP,DBP,MAP, HR,SaO2,RR,Pain score?) every 3-5 min		х	х	х	х						
Epidural Placement		Х									
Administration of Pre-op sedation			х								
Prep and supply of test drug			Х								
Infusion of Study drug if randomized for test group				х							
Infusion of Ropivacaine				х							
Primary measurements every 15 min						х	х				
(Secondary measurements) Sensory block assessment (1 hour post-op and every 6 hours for the subsequent 72 hours						x	х		x	x	x
Intra-op surgical records					Х						
Anesthesia Pain Service records			х	х	х	х	х	х	х	х	х
Pain Scores DVPRS Score							Х		Х	Х	Х
Record 24 hour I/Os						Х			Х	Х	Х
Pain management and "Rescue Drug" administration as needed							х	х	х	х	х
Record opioid usage						Х	Х	Х	Х	Х	Х
All SOC points and monitors: EKG, non-invasive BP; ETCO2; pulse ox; arterial line with Flow Track (if indicated); peripheral or central venous line; induction and mode of anesthesia.		x									
Physical therapy rehabilitation records (Time and distance of ambulation)									x	х	х

Patients will be approached about their willingness to participate in this study either in a pre-operative surgical or anesthetic clinic visit or in the pre-operative area on the day of surgery. Consent will be obtained by a member of the research team. The patient will be given time to read the consent, have all study related questions answered, and discuss the study with their family, if desired. A copy of the signed consent will be placed in the patient's physical chart, and a research progress note documenting study enrollment will be made in the patient's electronic medical record.

Inclusion criteria:

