Immediately following the establishment of an appropriate level for the planned surgery, an infusion of the test drug will be initiated at 4 to 8 mL per hour with a 4- to 8-mL patient-initiated bolus at a lockout interval of 1 hour – typically 8 mL per hour for major abdominal or thoracic surgery and thoracic epidural placement and 4 mL per hour for hip arthroplasty and lumbar epidural. Once established as effective for the clinical situation, this infusion will be left unchanged throughout the surgery and postoperative period. If clinically indicated, and the infusion rate is changed to below the limits of 4 – 8 mL per hour, this indicates the end of the need for the epidural infusion or otherwise untreatable hypotension.

Standard of Care - Intraoperative and Postoperative Periods:

Intraoperative and postoperative fluid management will be at the discretion of the anesthesia and primary teams.

Preoperative sedation will be a maximum of 5 mg of midazolam by intravenous injection (IV) and alfentanil 2000 mcg IV. Monitors include: EKG, non-invasive blood pressure, ETCO2, pulse oximeter, arterial line with Flow-Track (if indicated and appropriate per intra- or postoperative operative anesthesiologist), peripheral intravenous or central venous line as deemed appropriate by the attending intra- or postoperative operative anesthesia and mode of anesthesia (maintenance, fluid management, intraoperative analgesia, muscle relaxation, etc., are at the discretion of the attending intraoperative anesthesiologists.

If hypotension (see definition below) is encountered intraoperatively, the attending anesthesiologist will start a vasoactive or positive inotropic medication as indicated by the patient's medical requirements.

Research-Related Procedures – Intraoperative:

- Anesthesiologists will be encouraged to use alpha agonists if the other causes of hypotension are excluded and lumbar epidural is judged to be a contributory cause of the hypotension; and epinephrine, dobutamine, or dopamine (or indirect inotropic agents such as ephedrine) if thoracic epidural is judged to be the cause of the hypotension and the other causes of hypotension such as hypovolemia have been ruled out.

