- The epidural infusion will be continued intraoperatively at a rate 4 to 8 mL per hour. Emergence medications will be administered and recorded as judged appropriate by the intraoperative anesthesiologist. A bolus of 5 mL of ropivacaine 0.5% without additives may be administered through the epidural catheter at the conclusion of the intraoperative phase by the intraoperative anesthesiologist or APS anesthesiologist in the recovery room, if required.
- "Rescue" drugs as outlined below will be administered and recorded if deemed necessary. If, after sensation level testing, the epidural block was not appropriately covering the area of surgery, a further bolus of 5 mL of 0.5% ropivacaine will be injected by the APS physician and if this was still not managing the pain, this will be noted and the patient will be removed from the study. If judged appropriate by the APS physician, the epidural will either be replaced in the recovery area or the "rescue" medication described below will be initiated.
- Hypotension is defined as SBP > 20% below the baseline in the block room area before the epidural or sedation for the epidural was administered or an MAP less than 55 mmHg. Epidurals will be turned down or turned off if the treating Intensive Care Primary Physician declared it an emergency, if the patient had hemodynamic instability stemming from other causes that was complicated by the sympathetic block of the epidural, or significant hypotension, or mean MAP <

30%, from baseline and other causes such as hypovolemia had been corrected. If this is the case, the patient will be removed from the study.

Research-Related Procedures - Postoperative Periods:

If additional pain management or "rescue" analgesics are needed, for example, from outside the area covered by the epidural; subjects may receive any of the following:

- Acetaminophen (Tylenol) 1000 mg scheduled intravenously every 8 hours for the first 48 hours and, after oral intake is restarted, it will be changed to 1 gram every 6 hours by mouth (patients with liver disease will be excluded if appropriate and after discussion with the hepatic surgeon)
- Ketorolac Tromethamine (Toradol) 30 to 60 mg every 6 hours intravenously
- Celecoxib (Celebrex) 100 mg per mouth every 12 hours
- Oxycodone 5 to 10 mg per mouth every 4 hours as needed
- Intravenous hydromorphone (Dilaudid) patient-controlled analgesia (PCA) as per APS routine protocol appropriate for age and body habitus of the patient.

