Primary measurements:

Include the average invasively or non-invasively measured SBP, diastolic blood pressure (DBP), MAP, arterial blood oxygen saturation (SaO2), heart rate, respiratory rate, and pain by the visual analog pain score (VAS) on the "Defense and Veterans Pain Rating Scale" (DVPRS) measured over the following set periods:

Preoperative period

Primary measurements every 3 to 5 minutes and at indicated time points:

- I. Before the bolus epidural is injected.
- II. After the epidural bolus is injected but before anesthesia is induced.

Intraoperative period

Primary measurements every 3 to 5 minutes

Postoperative period

I. Primary measurements in the recovery room (if appropriate) every 15 minutes

II. Primary measurements following transfer to the floor every 4-6 hours if within normal limits, but every hour if needed for closer observation in case of possible abnormality for as long as the epidural analgesic blocks are continued, but at least every 8 hours after discharge from the PACU.

Secondary measurements:

[figure not shown]
- III. Spread of block per spinal root segment as tested by sensitivity to cold recorded every hour postoperatively and every 8 hours for the subsequent 72 hours after discharge from the PACU.
- IV. Ambulation on the first day after surgery (POD 1), POD 2 and 3, will be recorded per physical therapy protocol and distance ambulated per 24hour period will also be recorded. Physical Therapy information will be gathered to test motor effect on lumbar epidurals.
- V. Opioid usage data will be recorded and converted to morphine equivalents and averaged for POD 0, 1, 2, and 3 per group.
- VI. Side effects such as pruritus, nausea/vomiting, and respiratory depression (defined as respiratory rate less than 10 breaths per minute of oxygen saturation more than 7 points lower that the patients preoperative value on room air) will be recorded and managed as deemed appropriate by the attending physician.
- VII. 24 hour I/O for the first 72 hours to assess fluid balance, length of stay, and amount of days before return to PO status.

Data analysis plan

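### Opioid use is averaged by post-operative day with no hour windows, so POD 0 covers unequal time between patients and the early opioid comparison loses precision

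*Combined protocol and SAP*

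**What the plan says.** The opioid measure is defined in one sentence (Section 6, Secondary measurements, item V): use is expressed as morphine equivalents and "averaged for POD 0, 1, 2, and 3 per group". No POD is given in hours. Item IV fixes the numbering: "Ambulation on the first day after surgery (POD 1), POD 2 and 3". POD 0 is therefore the day of surgery.

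Other entries in the same list are tied to hours. Item VII records "24 hour I/O for the first 72 hours to assess fluid balance, length of stay", and item IV takes walking distance per 24 hours.

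As far as the broken activity table can be read, the row "Record opioid usage" is marked at PACU, one hour post-op, transfer to floor and POD 1 to 3. The intraoperative column is not marked. The plan allows a preoperative opioid on the same day ("alfentanil 2000 mcg IV", as a maximum) and does not say whether it counts in POD 0.

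Patients can leave observation early. Length of stay is recorded as an outcome. When the epidural is turned down or off for instability or hypotension, the plan says: "If this is the case, the patient will be removed from the study". Patients with a failed block are also removed. No rule covers the later opioid data of any of these patients.

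The Data analysis plan specifies the repeated-measures mixed model for continuous primary outcomes. It names no model for opioid use.

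**The concern.** Specific aim 1e asks whether epinephrine lowers opioid consumption. A POD 0 total mixes two things: how much opioid a patient needs per hour, and how many hours of the day remained after surgery. The second has nothing to do with treatment. Averaging such totals adds variance to the first post-operative period, and the resulting mean number of milligrams refers to no definite length of time.

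On later days the question is who contributes. If the daily average is taken over whoever has data, and discharge or removal differs by arm, the arms are compared on different kinds of patients. Removal for hypotension could differ by arm, because hypotension is what the epinephrine dose is meant to change.

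**Working it through.** **1. Is POD 0 a part-day?** Four periods of 24 hours (POD 0 to 3) would span 4 × 24 = 96 hours. Items III and VII follow patients for 72 hours, which is 3 × 24 and matches POD 1 to 3. The activity table lists the PACU, one-hour and transfer recordings apart from POD 1 to 3. POD 0 is then what remains of the day of surgery. If it ends at midnight, surgery ending at 10:00 leaves 14 hours and surgery ending at 20:00 leaves 4, a 3.5-fold range.

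**2. The plan's own figure.** No power figure is given for opioid use. The only one that could apply is the generic Cohen's f = 0.24 for group means (n = 200, 50 per group, 80% power, alpha 0.05). A one-way ANOVA with the four groups that these numbers imply gives f = 0.236 at 80% power, and 81.5% power at f = 0.24, so the figure reproduces. (Section 6 lists only three groups; that is a separate matter.)

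**3. Precision cost for POD 0.** The documents give no surgery end times and no spread of opioid use, so all inputs here are assumptions. Let use = hourly rate × hours, independent, with coefficients of variation CVr and CVt. Then Var(use)/mean² = CVr² + CVt² + CVr²·CVt². For a fixed window of the same mean length it is CVr². The ratio is

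inflation = 1 + CVt² × (1 + 1/CVr²), and effective sample loss = 1 − 1/inflation.

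For hours uniform on 4 to 14, the mean is 9, the SD is 10/√12 = 2.887, CVt = 0.321 and CVt² = 0.1029. With CVr = 0.6, inflation = 1 + 0.1029 × 3.778 = 1.389 and the loss is 28%.

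| POD 0 length | CVt | Loss, CVr 0.6 | CVr 0.8 | CVr 1.0 |
|---|---|---|---|---|
| 6-12 h | 0.192 | 12% | 9% | 7% |
| 4-14 h | 0.321 | 28% | 21% | 17% |
| 2-16 h | 0.449 | 43% | 34% | 29% |

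For 4-14 h, 200 patients are worth 200/1.389 = 144 (CVr 0.6) to 200/1.206 = 166 (CVr 1.0). Power at f = 0.24, with f scaled to the fixed-window SD, falls from 81.5% to about 66-73%.

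**4. Front-loaded use.** If the hourly rate decays with a half-life of 6 to 12 hours (assumed), late hours add less. For 4-14 h, CVt of the accumulated use is then 0.197 to 0.252, and the loss is 7-19%.

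**5. Cumulative totals.** Constant rate, 4-14 h, and POD 1 to 3 taken as full days:
- POD 0-1: mean 33 h, CVt² = 8.333/33² = 0.00765, loss 1.5-2.8%.
- POD 0-3: mean 81 h, CVt² = 8.333/81² = 0.00127, loss 0.2-0.5%.

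**6. Who contributes later.** Invented example: half the patients use 30 mg a day and half 10 mg, so the true mean is 20 mg. If 10%, 20% or 30% of patients leave, all lighter users, the mean of those remaining is (15 + (0.5 − p) × 10)/(1 − p) = 21.1, 22.5 or 24.3 mg. Two arms with equal need would differ by 24.3 − 21.1 = 3.2 mg if 30% left one and 10% the other. They would not differ if the same share left both.

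**The case against.** - **Calendar days are not stated.** A reader might infer that all four PODs are calendar days. The documents do not say so. Item IV links POD 1 to 3 with a 24-hour distance, and the activity table puts 24-hour intake and output under POD columns, so POD 1 to 3 may be 24-hour blocks. This stands. It does not rescue POD 0, which remains a part-day on the 72-hour count. The contrast with intake and output is also limited, since that window has no stated time zero either.
- **An available-case average is not stated.** A reader might infer that the POD 2 and 3 averages cover only patients still in hospital. The plan is silent on use after discharge. The finding is that no rule exists. Early discharge is also not the only route out, because the plan itself removes patients for failed block and for hypotension or instability.
- **Unequal POD 0 is noise.** A reader might infer that it biases the arm comparison. It does not, because end-of-surgery time is balanced by randomization in expectation. This stands in full.
- **The size is assumed and local.** No input to the precision figures comes from the documents, front-loading shrinks them, and cumulative totals are hardly affected. Aim 1e does not single out POD 0, and the activity table appears to record early use separately at PACU and one hour. This stands, and it limits the point to the early comparison.
- **Fixed windows do not recover lost patients.** This is correct: a 48-72 hour window loses the same people. A stated missing-data assumption is needed as well.

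**Conclusion.** The point holds as a precision and definition problem in a secondary outcome. If the plan is followed as written, the POD 0 opioid comparison is noisier than it need be. With constant hourly use and a between-patient CV of 0.6 to 1.0, the effective sample loss is 17-28% for a 4-14 hour POD 0, 7-12% for 6-12 hours and 29-43% for 2-16 hours. With front-loaded use, 4-14 hours costs 7-19%. Totals over POD 0-1 or longer lose under 3%. All of these rest on assumed hours and spreads.

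The documents do not support a claim of bias from the unequal POD 0. Bias on later days is possible only if discharge or removal differs by arm and the analysis drops those patients. The plan leaves that open, and the documents give no rate from which to size it.

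**What to change.** In item V, replace the POD averages with total morphine equivalents in 0-24, 24-48 and 48-72 hours from end of surgery, built from recorded administration times. Report preoperative and intraoperative opioids as separate lines outside these windows.

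In the Data analysis plan, extend the repeated-measures mixed model already specified for primary outcomes to the three windows. Include the available data of patients discharged early or removed from the study, state the missing-data assumption, and report how many patients contribute to each window by arm.

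The cost is small. Section 7 lists drug amounts and times of administration among the data collected. Because the activity table records opioid use by visit or day, some totals may have to be re-extracted from the medication record. Use after discharge may remain missing, and the windows alone do not cure that. No extra patients or procedures are needed.

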A limiting factor in the use of epidural analgesia, however, is the high incidence of associated hypotension. Hypotension is defined as systolic blood pressure (SBP) > 20% below the baseline preoperative measurements and acquired before the epidural or any sedation has been administered. Effective segmental epidural block would thus invariably cause sympathectomy due to its location in the thoracic or lumbar areas by blocking the cardiac sympathetic nerves, the pre-ganglionic nerves to the adrenal glands or the sympathetic nerves to the blood vessels individually or in combination.

It has been proven beyond doubt that epinephrine, when added to ropivacaine 0.2% and used for epidural analgesia by infusion, is safe and may even improve spinal cord blood flow and the analgesic effects of ropivacaine.⁷ It is also known that the cause of hypotension associated with epidural analgesia is the blockade of the sympathetic outflow to the cardiovascular and adrenal systems, and that the ideal mechanism to counter this would be by beta1-stimulation, which is ideally achieved with low-dose epinephrine.

Finally, it is known that epidural infused epinephrine increases its serum concentration.⁸ What is not known is whether added epinephrine will counteract this sympathetic blockade and prevent hypotension, and what the optimal concentration of epinephrine infusion would be during epidural analgesia with 0.2% ropivacaine to achieve optimal analgesia and optimal hemodynamic status.

5. Specific Aims:

We aim to examine whether adding epinephrine will counteract the sympathetic blockade and prevent hypotension, and what the optimal concentration of epinephrine infusion would be during epidural analgesia with 0.2% ropivacaine that can achieve both optimal analgesia and optimal hemodynamics. Specifically we plan to answer the following questions:

- 1. Does the addition of epinephrine to the epidural infusion of 0.2% ropivacaine:
 - a. Prevent hypotension?
 - b. Lead to a wider spread of local anesthetic effect?
 - c. Lead to a difference in the average pain scores?
 - d. Lead to a difference in when ambulation occurs?
 - e. Decrease potential of other opioid-related side effects such as pruritus, nausea/vomiting, respiratory depression and opioid consumption?
- 2. What is the optimal concentration of epinephrine (2mcg/mL or 5mcg/mL) to achieving the above-mentioned outcomes?

6. Research Plan:

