All data will be entered securely using the online database or Red Cap. To assess potential dose-response effects on changes in continuously measured primary outcomes, repeated measures mixed modeling analyses will be used. This type of analysis can assess the main effects of time (i.e., change) and group (i.e., epinephrine dose; coded as an ordinal variable) on the outcomes. Mixed models are the preferred approach to analyze data with repeated measures; these models can account for correlation among repeated measurements, flexible time effects, and can handle missing data. Additionally, this model can estimate time × group interactions. If this interaction is statistically significant, that provides evidence that the changes in outcomes are different depending on the dose of epinephrine that a patient received. Logistic regression models will be used to assess the relationship between epinephrine dose and incidence of hypotension (SBP < 20% or MAP < 55 mmHg) and other categorical outcome variables. A P value of <0.05 was considered statistically significant for all statistical tests. All analyses were conducted in JMP Pro 11.0 (SAS Institute, Cary, NC).

Sample size determination

At 80% power (alpha = 0.05), a sample of n=200 (50 per group) will be able to detect 26% differences in incidence of categorical outcomes, and an effect size of Cohen's f = 0.24 for group mean differences and effect size of Cohen's f = 0.09 for group differences mean change over time. Figure 1 depicts how these effect sizes will translate to the outcomes, with assumed standard deviations in outcomes ranging from 5 to 25. For example, assuming MAP has an SD = 10, the present study will be able to detect mean differences of 5 mmHg across groups and group differences of 3 mmHg for mean change over time.

ADMINISTRATIVE RESPONSIBILITIES:

Study Resources: The principal investigator will oversee the data collection, data analysis and will maintain the records in confidence. Should any evidence suggest that the study protocol require modification, the PI will notify the IRB in a timely manner for review and approval. Each subject will be identified by number, not by name, on all data forms. To protect confidentiality, all data will be numerically coded and information linking the numeric codes to individual participant's names will be kept in a locked file in the PI's office.

7. Possible Discomforts and Risks:

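### Aim 1d asks when ambulation occurs, but ambulation is recorded only on POD 1 to 3 and no method covers patients who have not walked by then

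*Combined protocol and SAP*

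**What the plan says.** Section 5 (Specific Aims) lists five questions about adding epinephrine. Question 1d is "Lead to a difference in when ambulation occurs".

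The data for it are described in section 6, Secondary measurements, item IV: "Ambulation on the first day after surgery (POD 1), POD 2 and 3, will be recorded per physical therapy protocol". Distance walked per 24 hours is recorded as well. The schedule of activities has a matching row, "Physical therapy rehabilitation records (Time and distance of ambulation", marked under POD 1, POD 2 and POD 3. POD 3 is the last column of the schedule.

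Item V, opioid use, covers a wider span: it is "averaged for POD 0, 1, 2, and 3 per group".

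Item VII reads "24 hour I/O for the first 72 hours to assess fluid balance, length of stay, and amount of days before return to PO status". The schedule has a row "Record 24 hour I/Os", marked for the PACU and POD 1 to 3, but no row for length of stay or return to oral intake.

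In the data analysis plan, "repeated measures mixed modeling analyses will be used" for continuously measured primary outcomes. Logistic regression is assigned to the incidence of hypotension "and other categorical outcome variables". No time-to-event method is named, and there is no rule for a patient who has not reached a milestone when recording stops.

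**The concern.** The time to a first walk is measured from surgery to an event. A recording window that opens on POD 1 and closes on POD 3 cuts it at both ends.

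The early end matters because the abstract's rationale cites a study in which epinephrine brought mobilisation forward. If the expected benefit exists, part of it may fall on a day when nothing is scheduled. The late end matters because the slowest patients would have no time at all, and with no stated rule the analyst would choose how to handle them after seeing the data. The question put in Aim 1d could then not be answered properly for the earliest and latest walkers.

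**Working it through.** The plan gives no figure for this outcome, so there is none to reproduce. The stated sample size and detectable effects do not bear on it. The check is a comparison of the text, followed by a labelled illustration.

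**Step 1. Windows side by side.**

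| Item | Days named in the text | Schedule |
|---|---|---|
| Ambulation (IV) | POD 1, 2, 3 | POD 1, 2, 3 |
| Opioid use (V) | POD 0, 1, 2, 3 | PACU to POD 3 |
| 24-hour I/O (VII) | first 72 hours | PACU, POD 1, 2, 3 |
| Length of stay, days to oral intake (VII) | none of their own | no row |

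Text and table agree on ambulation, so the window is not an artefact of a damaged table. Item V shows that the authors treat POD 0 as a separate day. It is named there and not in item IV.

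**Step 2. Three patients followed through the plan as written.**

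- First walk on POD 0: no record is scheduled. The earliest possible record is on POD 1, so this patient cannot be told from one who first walked on POD 1.
- First walk on POD 2: captured, with a time if the schedule row means clock time. The row's wording could also mean duration, and the protocol does not say which.
- First walk after POD 3: no record. This patient cannot be told from one who never walked.

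**Step 3. Analysis.** The mixed models are for continuous primary outcomes and the logistic models for categorical ones. Time to first walk is a secondary outcome that is unobserved for some patients. Neither sentence says how the third patient enters a comparison.

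**Step 4. Illustration of the late end, on assumption only.** Suppose that time to first walk is lognormal with log-SD 0.5 and median *m* days. The share still not walking at *c* days is 1 − Φ((ln *c* − ln *m*)/0.5). POD 3 ends between 3 and 4 days after surgery, so both are shown.

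| Median *m* | Share after *c* = 3 | Share after *c* = 4 |
|---|---|---|
| 1.5 days | 1 − Φ(1.386) = 8% | 1 − Φ(1.962) = 2% |
| 2 days | 1 − Φ(0.811) = 21% | 1 − Φ(1.386) = 8% |
| 3 days | 1 − Φ(0) = 50% | 1 − Φ(0.575) = 28% |

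The loss could be trivial or large, depending on a median that the documents do not supply. No comparable figure is offered for POD 0, because nothing in the documents describes how soon patients are mobilised.

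**The case against.** The strongest reply is that the window is a deliberate and coherent choice. The sensory block is also followed for 72 hours, the study concerns the period of the epidural infusion, and the schedule records time as well as distance, so timing is captured inside the window. Ambulation is one secondary item among several. The walking times may also sit in the medical record and be recoverable. A logistic model of having walked by a given POD would avoid the need for exact times.

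Part of this stands. The window suits distance walked, and recoverable data make the repair cheap. But a yes/no analysis by POD is not specified for ambulation, it would still misclassify a patient who walked on POD 0 and not on POD 1, and Aim 1d asks when, not whether. That data may exist elsewhere is a reason to say in the protocol that they will be used.

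Two stronger readings are tempting and should not be drawn:

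- A reader might infer from item VII that length of stay and return to oral intake are recorded only within 72 hours. The documents do not say so. The 72 hours directly qualifies the I/O record, and the other two can be read as separate list items with no cut-off. A stay ends at discharge by definition, and a missing schedule row shows an incomplete table, not truncated data. Any estimate of the share of stays running past day 3 would measure a cut-off that is not established.
- A reader might infer that the observed walking times will simply be averaged, with slow patients dropped unequally by arm. The plan prescribes averaging for opioid use, not for ambulation. The fair criticism is that no method is stated.

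**Conclusion.** The point holds for ambulation. The stated recording window truncates the outcome that Aim 1d names: POD 0 walks appear late, first walks after POD 3 have no time, and no analysis rule covers patients who have not walked by then. This conclusion rests on the text alone. Its size is unknown, because the documents give no distribution for time to first walk, and the percentages above only show how strongly the answer depends on an assumed median. The primary measurements and the sample size are unaffected.

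For length of stay and days to oral intake, the finding is limited to unclear wording: neither source nor end of follow-up is stated.

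**What to change.** - **Definition.** In item IV, define time to first ambulation as hours from end of surgery to the first recorded walk. Take it from existing physical therapy and medical records, from POD 0 to discharge. Keep distance on POD 1 to 3.
- **Population.** Collect it for every randomised patient, including those whom section 6 removes from the study for block failure, inadequate cover or haemodynamic reasons.
- **Schedule.** Add POD 0 to the ambulation row, add a chart review at discharge, and say that time means clock time.
- **Analysis.** Add a time-to-event comparison of the arms to the data analysis plan. Count patients without a recorded walk as not having walked by the end of follow-up. Discharge may itself depend on walking, so treating it as uninformative censoring is doubtful. Add a sensitivity analysis that varies how patients discharged without a recorded walk are handled.
- **Item VII, wording only.** State that length of stay and days to oral intake are taken to discharge, and keep 72 hours for the I/O record.

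The cost is one chart review per patient at discharge and a few lines of text, with no added visit or procedure. Some POD 0 charting will be incomplete, and the report should say how often.

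### The plan does not say how pre-infusion blood pressure enters the mixed model or when hypotension starts to count; adjusting for it and analysing only post-infusion data would usually gain power at little cost

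*Combined protocol and SAP*

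**What the plan says.** The Data analysis plan uses a repeated-measures mixed model for the continuous outcomes. Its named terms are time, dose group and their interaction: "This type of analysis can assess the main effects of time (i.e., change) and group", and "If this interaction is statistically significant, that provides evidence that the changes in outcomes are different depending on the dose of epinephrine". It names no covariate, no reference time point and no primary term. A logistic model relates dose to "incidence of hypotension (SBP < 20% or MAP < 55 mmHg) and other categorical outcome variables", with no start or end of counting.

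Some primary measurements precede the randomised drug. The schedule of activities (section 6) lists "Primary measurements(SBP,DBP,MAP, HR,SaO2,RR,Pain score?) every 3-5 min" at the pre-op baseline, after epidural placement but before the bolus, and after the bolus. Under Primary measurements, one preoperative time point is "Before the bolus epidural is injected". The preoperative sections start the test infusion only after the bolus has produced a suitable block.

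A clean baseline is defined. Section 4 refers hypotension to "baseline preoperative measurements and acquired before the epidural or any sedation has been administered", and the intraoperative procedures use "SBP > 20% below the baseline in the block room area before the epidural or sedation for the epidural was administered". The plan uses this value only as the reference for the 20% criterion.

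**The concern.** A reading taken before the infusion starts cannot carry a drug effect. Kept as an outcome row, it dilutes the group main effect. As a covariate, it removes between-patient variation. If it is left out, that information is lost. These choices differ widely in power, and the text allows any of them to be made after the data are seen.

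Hypotension has a parallel gap. Its reference value precedes sedation, the test dose and the main bolus, and all of these come before the study infusion. A fall in pressure caused by the bolus could therefore count as an event, although the study drug could not have prevented it. Such events occur equally in all arms and shrink the difference the trial hopes to detect. Preventing hypotension is the first question in the Specific Aims.

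**Working it through.** **The plan's own figures.** A one-way ANOVA with N = 200 in four groups, alpha 0.05 and 80% power gives a detectable f of 0.236, which matches the stated 0.24. In mmHg this is 2 × 0.236 × 10 = 4.7, close to the stated 5. With the three listed groups of 50, detectable f is 0.256. The f of 0.24 uses no baseline information. The f of 0.09 for change is reproduced only with assumed inputs (correlation 0.5: 0.094 with five occasions, 0.089 with six).

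**Inputs.** From the documents: 50 per arm, SD 10, a 5 mmHg difference, alpha 0.05. Assumed: three arms, constant post-infusion means 0/2.5/5, exchangeable correlation ρ of 0.3, 0.5 or 0.7, q = 1 or 2 pre-infusion periods, s = 3 or 4 post-infusion periods, and dose tested on 2 df. The sum of squared centred means is S = 2.5² + 0 + 2.5² = 12.5, so nS = 625.

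**Formulas.** Let m = q + s and v_j = (1 + (j − 1)ρ)/j. The noncentralities are:
- group main effect, all rows: 625 (s/m)² / (100 v_m)
- time by group: 625 s(1 − s/m) / (100(1 − ρ)), on 2(m − 1) df with categorical time or 2 df with time coded pre/post; error df 147(m − 1)
- post-infusion only: 625 / (100 v_s)
- adjusted for one baseline: 625 / (100(v_s − ρ²)), error df 146
- adjusted for the mean of q pre-readings: 625 / (100(v_s − ρ²/v_q)), error df 146

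**Example: ρ = 0.5, q = 2, s = 3.**
- Main effect: 625 × 0.36 / 60 = 3.75, power 39%.
- Interaction: 625 × 1.2 / 50 = 15, power 79% (categorical time) or 94% (pre/post).
- Post-infusion only: 625 / 66.7 = 9.375, power 78%.
- One baseline: 625 / 41.7 = 15, power 94%.
- Mean of two: 625 / 33.3 = 18.75, power 98%.

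**Power over the grid (%).**

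| Analysis | ρ = 0.3 | ρ = 0.5 | ρ = 0.7 |
|---|---|---|---|
| Main effect, pre-rows kept | 51-77 | 39-62 | 31-52 |
| Time × group, categorical time | 42-63 | 58-81 | 84-97 |
| Time × group, pre/post, one pre-reading | 63-66 | 78-81 | 95-96 |
| Time × group, pre/post, two pre-readings | 84-88 | 94-96 | 99.6-99.8 |
| Post-infusion only | 87-91 | 78-81 | 70-71 |
| Post-infusion, block-room baseline | 92-96 | 94-96 | 98-99 |
| Post-infusion, mean of two pre-readings | 95-98 | 98-99 | 99.8-99.9 |

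**Low baseline correlation.** Let b be the baseline-post correlation, so the adjusted variance is v_s − b². At b = 0.1-0.2 with post-post correlation 0.3-0.7, adjustment gains 0.6-2.7 points over post-infusion only.

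**Hypotension.** Assume post-infusion incidence 50/37/24%. The 26-point spread is the plan's figure ("will be able to detect 26% differences in incidence of categorical outcomes"); the control rate is assumed. If a share p0 of every arm qualifies before infusion, independently of later events, the counted incidence is p0 + (1 − p0)p and the difference is 26(1 − p0) points. Power is simulated for a logistic model with dose linear by rank, likelihood-ratio test, 50 per arm.

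| p0 | Difference (points) | Power |
|---|---|---|
| 0% | 26.0 | 78% |
| 2% | 25.5 | 76% |
| 5% | 24.7 | 73% |
| 10% | 23.4 | 68% |
| 20% | 20.8 | 57% |
| 30% | 18.2 | 47% |

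**The case against.** The strongest reply is that the plan speaks of change and of time by group, so baseline already enters through the interaction. That is the natural reading. With the two pre-bolus readings the schedule provides, a pre/post-coded interaction does well: the block-room covariate alone leads it by about 8 points at ρ = 0.3 (92.5 − 84.1 and 95.6 − 87.9), ties at 0.5 and trails by about 1 point at 0.7. A reader might infer that a single-baseline covariate always wins, or that gains of 15 to 30 points are typical. The schedule does not support that, since gains of that size over the pre/post interaction need a single pre-reading. Adjusting for the mean of both readings is, however, at least as powerful as that interaction in every cell. The plan also does not commit to pre/post coding, names the main effect alongside, and sizes the trial on both.

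Three further objections stand as limits. The correlation is unknown and could be low, because baseline is taken awake and later readings follow sedation, block, anaesthesia and discretionary treatment. The absolute powers depend on unsettled inputs: if the stated 200 were split over three arms, post-infusion-only power would be 83-97%. And 3 mmHg, the plan's target for change, was not tested here.

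On hypotension, the pre-infusion window may be short, because the infusion follows the block at once. The definition also sits under intraoperative procedures. Both make a small p0 plausible, but neither sets a window.

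**Conclusion.** The point holds as a matter of efficiency and prespecification. A reader might infer that the planned analysis is biased or the trial invalid. The documents do not support that: the study drug cannot affect pre-infusion readings or events, and randomisation keeps every one of these comparisons valid. Nor do they show that pre-infusion hypotension will be counted, only that nothing excludes it.

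Under the stated assumptions, the analyses the text permits range from 31% to above 99% power for the same 5 mmHg effect. The block-room-adjusted analysis stays at 92% or above throughout ρ = 0.3-0.7. That advantage shrinks to about 1-3 points over post-infusion readings alone if baseline is weakly correlated with what follows. The hypotension loss is minor at a pre-infusion rate of 2-5% and substantial at 10-30%; the documents give no rate. The change is worth making because it costs so little.

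**What to change.** State in the Data analysis plan:

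1. **Covariate.** Blood pressure before the bolus enters the mixed model as a covariate: either the defined block-room baseline or, where both scheduled pre-bolus readings exist, their mean. Write down which one in advance. The block-room value stays the reference for the 20% SBP criterion.
2. **Outcome rows and primary test.** Only readings after the study infusion starts are outcome rows. The dose-group difference averaged over them is the primary dose test, and time by group over the same rows is secondary.
3. **Hypotension window.** Count only episodes that begin after the study infusion starts. An episode already under way at that moment is not counted unless pressure recovers and falls again.

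The cost is analysis-plan wording and one degree of freedom, with no added visits or patients. The after-bolus period must be split at infusion start, which needs the infusion start time and individually timed blood pressures. Section 7 lists drug-administration times among the collected data. Primary measurements speaks of averages over periods, so the plan should confirm that timed readings are kept.
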